### **14.1 Protocol amendments**

Any change or addition to the protocol can only be made in a written protocol amendment that must be approved by Novartis, health authorities where required, and the IRB/IEC prior to implementation.

Only amendments that are required for participant safety may be implemented immediately provided the health authorities are subsequently notified by protocol amendment and the reviewing IRB/IEC is notified.

Notwithstanding the need for approval of formal protocol amendments, the investigator is expected to take any immediate action required for the safety of any participant included in this study, even if this action represents a deviation from the protocol. In such cases, Novartis should be notified of this action and the IRB/IEC at the study site should be informed according to local regulations.

## 16 Appendices

### 16.1 Appendix 1: Clinically notable laboratory values and vital signs

The central laboratory will flag laboratory values falling outside of the normal ranges on the central laboratory reports. Investigators are responsible for reviewing these abnormal values for clinical significance, signing the laboratory reports to indicate their review, and reporting values considered clinically significant in the appropriate eCRF. Any clinically significant abnormal laboratory value should be evaluated and followed-up by the investigator until normal or a cause for the abnormality is determined. See [Section 16.2](#) for specific liver event and laboratory test trigger definitions and follow-up requirements. See [Appendix 3](#) for specific renal alert criteria and actions. Post-baseline vital signs will be flagged as notable abnormalities as follows:

1. Systolic/Diastolic blood pressure:  $\geq 25\%$  decrease or  $\geq 25\%$  increase from baseline
2. Pulse:  $\geq 110$  bpm with  $\geq 15\%$  change from baseline, or  $< 50$  bpm with  $\geq 15\%$  change from baseline

## 16.2 Appendix 2: Liver event and laboratory trigger definitions & follow-up requirements

**Table 16-1 Liver Event Definitions**

| Definition                                   | Thresholds   |
|--|--|
| Potential Hy's law cases                     | ALT or AST > 3 × ULN and TBL > 2 × ULN without initial increase in ALP to > 2 × ULN  |
| ALT or AST elevation with coagulopathy       | ALT or AST > 3 × ULN and INR > 1.5 (in the absence of anticoagulation)   |
| ALT or AST elevation accompanied by symptoms | ALT or AST > 3 × ULN accompanied by (general) malaise, fatigue, abdominal pain, nausea, or vomiting, or rash, or eosinophilia  |
| Isolated ALT or AST elevation                | 

• ALT or AST > 8 × ULN

• 5 × ULN < ALT/AST ≤ 8 × ULN

• 3 × ULN < ALT/AST ≤ 5 × ULN

                |
| Isolated ALP elevation                       | ALP > 2 × ULN (in the absence of known bone pathology)   |
| Others                                       | 

• Any clinical event of jaundice (or equivalent term)

• Any adverse event potentially indicative of liver toxicity

 |

**Table 16-2 Actions required for Liver Events**

| Criteria   | Actions required  |
|--|---|
| Potential Hy's Law case  |   |
| ALT or AST elevation with coagulopathy   |   |
| ALT or AST elevation accompanied by symptoms   | 
 
• Discontinue the study treatment immediately
 
• Hospitalize, if clinically appropriate
 
• Establish causality
 
• Complete CRFs per liver event guidance*
 
   |
| Isolated ALT or AST elevation $> 8 \times \text{ULN}$  |   |
| Jaundice   |   |
| Isolated ALT or AST elevation $> 5 \text{ to } \leq 8 \times \text{ULN}$                           | 
 
• If confirmed, consider interruption or discontinuation of study drug
 
• If elevation persists for more than 2 weeks, discontinue the study drug
 
• Establish causality
 
• Complete CRFs per liver event guidance*
 
   |
| Isolated ALT or AST elevation $> 3 \text{ to } \leq 5 \times \text{ULN}$ (patient is asymptomatic) | Monitor liver chemistry tests two or three times weekly   |
| Isolated ALP elevation   | 
 
• Repeat liver chemistry tests within 48-72 hours
 
• If elevation is confirmed, measure fractionated ALP; if <math>>50\%</math> is of liver origin, establish hepatic causality
 
• Complete CRFs per liver event guidance*
 
 |
| Any AE potentially indicative of liver toxicity  | 
 
• Consider study treatment interruption or discontinuation
 
• Hospitalize if clinically appropriate
 
• Complete CRFs per liver event guidance*
 
  |

\*Liver event guidance for CRF completion is available in the CRF Completion Guidelines.

**Table 16-3 Exclusion of underlying liver disease**

| Disease                        | Assessment  |
|--------------------------------|---|
| Hepatitis A, B, C, E           | IgM anti-HAV; HBSAg, IgM anti-HBc, HBV DNA; anti-HCV, HCV RNA, IgM & IgG anti-HEV, HEV RNA                |
| CMV, HSV, EBV infection        | IgM & IgG anti-CMV, IgM & IgG anti-HSV; IgM & IgG anti-EBV  |
| Autoimmune hepatitis           | ANA & ASMA titers, total IgM, IgG, IgE, IgA   |
| Alcoholic hepatitis            | Ethanol history, GGT, MCV, CD-transferrin   |
| Nonalcoholic steatohepatitis   | Ultrasound or MRI   |
| Hypoxic/ischemic hepatopathy   | Medical history: acute or chronic CHF, hypotension, hypoxia, hepatic venous occlusion. Ultrasound or MRI. |
| Biliary tract disease          | Ultrasound or MRI, ERCP as appropriate.   |
| Wilson disease                 | Caeruloplasmin  |
| Hemochromatosis                | Ferritin, transferrin   |
| Alpha-1-antitrypsin deficiency | Alpha-1-antitrypsin   |

## 16.3 Appendix 3: Specific Renal Alert Criteria and Actions and Event Follow-up

**Table 16-4 Specific Renal Alert Criteria and Actions**

| Renal Event  | Actions   |
|--|---|
| Confirmed serum creatinine increase 25 – 49%   | 

Consider causes and possible interventions

Follow up within 2-5 days

  |
| Serum creatinine increase 50 % +
OR if <18 years old, eGFR 35 mL/min/1.73 m    | 

Consider causes and possible interventions

Repeat assessment within 24-48h if possible

Consider drug interruption or discontinuation unless other causes are diagnosed and corrected

Consider patient hospitalization and specialized treatment

 |
| New onset dipstick proteinuria $\geq 3^+$
OR
Protein-creatinine ratio (PCR) $\geq 1\text{g/g Cr}$ (or mg/mmol equivalent as converted by the measuring laboratory) | 

Consider causes and possible interventions

Assess serum albumin & serum total protein

Repeat assessment to confirm

Consider drug interruption or discontinuation unless other causes are diagnosed and corrected

                            |
| New onset hematuria $\geq 3^+$ on urine dipstick   | 

Repeat assessment to confirm

Distinguish hemoglobinuria from hematuria

Urine sediment microscopy

Assess sCr

Exclude infection, trauma, bleeding from the distal urinary tract/bladder, menstruation

Consider bleeding disorder

  |

+ Corresponds to KDIGO criteria for Acute Kidney Injury

Additional specialized assessments are available to assess renal function or renal pathology.  
*(Note: In exceptional cases, when a nephrologist considers a renal biopsy, it is recommended to make slide specimen available for evaluation by the RSG to potentially identify project-wide patterns of nephrotoxicity.)*

- Whenever a renal event is identified, a detailed patient history and examination are indicated to identify and potentially eliminate risk factors that may have initiated or contributed to the event:
- Blood pressure assessment (after 5-minute rest, with an appropriate cuff size)
- Signs and symptoms like fever, headache, shortness of breath, back or abdominal pain, dysuria or hematuria, dependent or periorbital edema
- Changes in blood pressure, body weight, fluid intake, voiding pattern, or urine output
- Concomitant events or procedures such as trauma, surgical procedures, cardiac or hepatic failure, contrast media or other known nephrotoxin administration, or other diseases or causes, e.g., dehydration due to delirium, tumor lysis

**Table 16-5      Renal Event Follow Up**

| FOLLOW-UP OF RENAL EVENTS  |
|---|
| 

• Urine dipstick and sediment microscopy evidence of DIN: crystals, red blood cells (dysmorphic/glomerular vs. non-dysmorphic/non-glomerular), white blood cells, tubular epithelial cells

• Blood pressure and body weight

• Serum creatinine, BUN, electrolytes (sodium, potassium, phosphate, calcium), bicarbonate and uric acid

• Urine output

                                       |
| Review and record possible contributing factors to the renal event (co-medications, other co-morbid conditions) and additional diagnostic procedures (MRI etc.) in the CRF  |
| 

• Event resolution: (sCr within 10% of baseline or PCR < 1 g/g Cr, or ACR <300 mg/g Cr) or

• Event stabilization: sCr level with <math>\pm 10\%</math> variability over last 6 months or protein-creatinine ratio stabilization at a new level with <math>\pm 50\%</math> variability over last 6 months.

• Analysis of urine markers in samples collected over the course of the DIN event

 |

## 1 Introduction

### 1.1 Scope of document

The Reporting and Analysis Plan (RAP) documents contain detailed information to aid the production of Statistics & Programming input into the Clinical Study Report (CSR) for trial “**CCMK389B12201**”.

The Statistical Analysis Plan (SAP) describes the implementation of the statistical analysis planned in the protocol.

### 1.2 Study reference documentation

Study Protocol v02 is available at the time of finalization of SAP.

### 1.3 Study objectives

#### 1.3.1. Primary objective

Primary objective	Endpoint for primary objective

To assess the efficacy of CMK389 in participants with moderate to severe atopic dermatitis (AD)

	

Investigator Global Assessment (IGA) response (defined as clear or almost clear and at least 2-point reduction from baseline) at Week 16

#### 1.3.2. Secondary objective

Secondary objective	Endpoint for secondary objective

To assess the safety and tolerability of CMK389 in participants with AD

	

Number, seriousness and frequency of adverse events over time.

Commercially Confidential Information

---

Commercially Confidential Information

Comercially Confidential Information

#### **1.4 Study design and treatment**

This is a randomized, placebo-controlled, parallel-group, non-confirmatory, investigator and participant blinded study in adult participants with moderate to severe AD. The study will randomize approximately 64 participants to the following four treatment arms in a ratio of 4:1:2:1 as follows:

- Arm 1: 32 participants treated intravenously (i.v.) with 10 mg/kg CMK389
- Arm 2: 8 participants treated i.v. with placebo
- Arm 3: 16 participants treated subcutaneously (s.c.) with 300 mg CMK389
- Arm 4: 8 participants treated s.c. with placebo

Comercially Confidential Information

---

Commercially Confidential Information

Comercially Confidential Information

## 4 Statistical methods: Analysis sets

For all analysis sets, participants will be analyzed according to the study treatment received. For participants for which the actual treatment received does not match the randomized treatment, the treatment actually received will be used for the analysis.

The safety analysis set will include all participants who received any study drug.

Comercially Confidential Information

The PD analysis set will include all participants who received any study drug and had no protocol deviations with relevant impact on PD data.

The analysis sets and protocol deviation codes are related as follows:

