## **2.1 Primary estimands**

The primary clinical question of interest is: What is the effect of the CMK389 treatment versus placebo on IGA response rate after 16 weeks of treatment in participants with moderate to severe AD without any relevant use of prohibited medication or use of rescue medication taken after the first 6 weeks.

Prohibited or rescue medication are relevant when their use may have a potential confounding effect on the efficacy assessment.

The justification for targeting this treatment effect is that we wish to estimate the effect of the study drug for the full duration when administered without any relevant use of prohibited medication or use of rescue medication taken after the 6 first weeks.

The primary estimand is described by the following attributes:

1. Population: Adult participants with moderate to severe AD is the target population for biologics ([Beck et al 2014](#), [Simpson et al 2016](#)) and is defined by an IGA score of moderate to severe (3 or 4) and an EASI score of at least 12. Further details about the population are provided in [Section 5](#).
2. Primary variable: IGA response (defined as clear or almost clear and at least 2 point reduction from baseline) at Week 16.
3. Treatment of interest: the randomized treatment (the investigational treatment CMK389 or the placebo treatment) taken for the entire study duration without any use of prohibited medications or use of rescue medication taken after the first 6 weeks.
4. The summary measure: Treatment difference of the CMK389 and placebo in absolute responder rates.

Handling of remaining intercurrent events:

1. Use of rescue therapy (after first 6 weeks of treatment)
2. Use of prohibited medication to treat AD symptoms or with impact on efficacy
3. Study treatment discontinuation due to lack of efficacy
4. Study treatment discontinuation due to AE related to AD, e.g. worsening of AD
5. Study treatment discontinuation due to AE not related to AD or due to lack of tolerability
6. Study treatment discontinuation due to other reasons (e.g. administrative if participant relocates to a region where the trial is not offered, or withdrawal of informed consent)

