#### 4.1 Rationale for study design

**Table 4-1 Rationale for study design**

|                              |   |
|------------------------------|---|
| Placebo controls      | 
The placebo group is used to define the natural history of disease under the study's conditions. Comparison of placebo to the active group provides the most rigorous test of efficacy. The comparison to placebo is being used for many studies including late stage development trials (Simpson et al 2016, Guttman-Yassky et al 2020a, Guttman-Yassky et al 2020b, Wollenberg et al 2019, Simpson et al 2019) to enable a rigorous and double blind comparison. In this study, placebo exposed participants are reduced to a quarter of overall study population.
 
Commercially Confidential Information
 
Participants may use emollients as basis therapy during the study, and may use oral antihistamines for symptomatic itch relief. If medically justified and disease severity is worsening, participants may use other rescue treatments (standard of care) as well.
                                  |
| Randomization         | Randomization is used to avoid "selection bias" in the assignment of participants to treatment groups. Randomization also serves to balance the treatment groups with respect to many known and unknown confounding variables; and randomization forms the basis of assumptions for our statistical tests. In this study randomization was set up so as to favor recruitment of participants in treatment arm 1 (CMK389 i.v. administration).   |

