### **12.1 Analysis sets**

For all analysis sets, participants will be analyzed according to the study treatment received.

The safety analysis set will include all participants who received any study drug.

The PK analysis set will include all participants with at least one available valid (i.e. not flagged for exclusion) PK concentration measurement, who received any study drug.

The PD analysis set will include all participants who received any study drug and had no protocol deviations with relevant impact on PD data.

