## **12.4 Analysis of the primary endpoint(s)/estimand(s)**

The primary aim of the study is to assess efficacy of CMK389 in participants with moderate to severe AD. This will be evaluated by assessing the IGA response at Week 16. This analysis will be performed on the PD analysis set. For the efficacy analyses, the two placebo groups (placebo s.c. and i.v.) will be pooled together.

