## **6 Statistical methods for Pharmacodynamic (PD) parameters**

### **6.1 Primary objective**

The primary objective of this study is to assess efficacy of CMK389 in participants with moderate to severe AD. This analysis will be performed on the safety analysis set.

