#### **6.1.1 Variables**

The primary variable is the IGA response at Week 16, defined as clear or almost clear at Week 16 with at least 2-point reduction from baseline.

The IGA rating scale is a Validated Investigator Global Assessment scale for Atopic Dermatitis (vIGA-ADTM) and it describes the overall disease severity for the whole body on a 5-point scale: clear (0), almost clear (1), mild (2), moderate (3), and severe (4).

For the descriptive analysis ([Section 6.1.2](#)) the placebo groups (i.e. placebo i.v. and placebo s.c.) will be presented both separately and pooled. For the inferential analysis ([Section 6.1.3](#)), the two placebo groups (placebo s.c. and i.v.) will be only presented pooled.

Baseline is considered to be the last assessment (including those from unscheduled visits) obtained before the first dose of study treatment.

The primary clinical question of interest is: What is the effect of CMK389 versus placebo on IGA response after 16 weeks of treatment in patients with moderate or severe atopic dermatitis without any relevant use of prohibited medication or use of rescue medication taken after first 6 weeks.

Prohibited or rescue medication are relevant when their use may have a potential confounding effect on the efficacy assessment.

This estimand will enable assessment of the effect of CMK389 for the full duration in the absence of relevant use of prohibited medication or use of rescue medication taken after the first 6 weeks.

The primary estimand is described by the following attributes:

**Population:** Adult participants with moderate to severe atopic dermatitis is the target population for biologics (Beck et al 2014, Simpson et al 2016) and is defined by an IGA score of moderate to severe (3 or 4) and an EASI score of at least 12 as defined by the study inclusion and exclusion criteria who were randomized to treatment. Further details about the population are provided in Section 5 of the protocol. This implies that analyses will be based on the safety analysis set.

**Endpoint:** IGA response at week 16, where IGA response is defined as clear or almost clear and with at least a 2-point reduction compared to baseline and no use of confounding therapy before the assessment time point.

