**Treatment of interest:** the treatment (the investigational treatment CMK389 or placebo) actually taken for the entire study duration without any use of prohibited medications or use of rescue medication taken after the first 6 weeks.

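### The primary efficacy analysis groups participants by treatment received, although the protocol's estimand is built on randomised treatment; the SAP changes the estimand to fit

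*SAP*

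**What the plan says.** Protocol 12.1 gives one grouping rule and makes no exception for efficacy: "For all analysis sets, participants will be analyzed according to the study treatment received". SAP section 4 repeats it and spells out the mismatch case: "For participants for which the actual treatment received does not match the randomized treatment, the treatment actually received will be used for the analysis".

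The primary IGA analysis falls under this rule in both documents. Protocol 12.4 states "This analysis will be performed on the PD analysis set"; SAP 6.1 states "This analysis will be performed on the safety analysis set". The two sets differ, which is a separate inconsistency, but participants in both are grouped by treatment received.

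The estimand reads differently. Protocol 2.1 gives the treatment of interest as "the randomized treatment (the investigational treatment CMK389 or the placebo treatment) taken for the entire study duration", and the protocol summary agrees. Protocol Table 4-1 adds that "randomization forms the basis of assumptions for our statistical tests". SAP 6.1.1 changes the treatment attribute to "the treatment (the investigational treatment CMK389 or placebo) actually taken for the entire study duration", while its population attribute still describes participants "as defined by the study inclusion and exclusion criteria who were randomized to treatment". SAP 1.1 describes the SAP's job as implementing the analysis that the protocol planned.

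**The concern.** A treatment-received rule is standard for safety and exposure data. For efficacy, it lets an event after randomisation decide in which group a participant and the outcome are counted. The groups compared are then no longer those formed by randomisation, which is the basis the protocol itself gives for its statistical tests.

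The two documents also carry different primary estimands. A reader of the protocol would expect wrongly dosed participants to stay in their randomised arm; a reader of the SAP would expect them to move. The visible text has no rule for a participant who receives only some wrong doses, although Protocol 9.1.1.1 refers to 4 planned doses. The powered comparison has 32 against 16 participants, so one person carries 1/32 = 3.1 points in the active arm and 1/16 = 6.3 points in pooled placebo.

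**Working it through.** **The plan's own figure.** Protocol 12.8.1 gives an 80% probability of meeting the dual criteria with 32 on CMK389 i.v. and 16 on pooled placebo, at true rates of 43% (7% + 36 points) and 7%. The thresholds and the placebo MAP prior are redacted, so this cannot be reproduced exactly. Simple stand-ins bracket it: normal approximation 77.7% (two-sided 0.05) and 88.0% (one-sided 0.05); Fisher's exact test 73.8% and 80.8%. The figure is plausible, and this point does not depend on it.

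**The texts compared.**

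| Item | Protocol | SAP |
|---|---|---|
| Treatment of interest | randomised treatment (2.1) | treatment actually taken (6.1.1) |
| Grouping rule | treatment received, all sets (12.1) | treatment received, mismatch case explicit (4) |
| Set for the primary analysis | PD set (12.4) | safety set (6.1) |

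The first two protocol entries disagree with each other. The SAP entries agree with each other only because the estimand was changed.

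**Moving one participant, raw rates.** The starting counts are assumptions near the planning rates: 14/32 active, with 1/16 placebo (2/16 where a placebo responder is needed). One participant is counted wholly in the other group.

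| Case | As randomised | As treated | Shift (points) |
|---|---|---|---|
| Active responder given placebo | 14/32 - 1/16 = 37.5% | 13/31 - 2/17 = 30.2% | -7.3 |
| Active non-responder given placebo | 37.5% | 14/31 - 1/17 = 39.3% | +1.8 |
| Placebo non-responder given i.v. active | 37.5% | 14/33 - 1/15 = 35.8% | -1.7 |
| Placebo responder given i.v. active | 14/32 - 2/16 = 31.2% | 15/33 - 1/15 = 38.8% | +7.5 |
| S.c. placebo responder given s.c. active (moves to the untested arm) | 31.2% | 14/32 - 1/15 = 37.1% | +5.8 |

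**With a placebo prior.** The prior's parameters are redacted. Assume Beta(0.07 × ESS, 0.93 × ESS) with effective sample size (ESS) 20 or 40, and keep the raw active rate. The placebo estimate is then (0.07 × ESS + responders)/(ESS + n).

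- Active responder given placebo. ESS 20: (14/32 - 2.4/36) = 37.1% against (13/31 - 3.4/37) = 32.7%, shift -4.3. ESS 40: (14/32 - 3.8/56) = 37.0% against (13/31 - 4.8/57) = 33.5%, shift -3.4.
- Placebo responder given i.v. active. ESS 20: (14/32 - 3.4/36) = 34.3% against (15/33 - 2.4/35) = 38.6%, shift +4.3. ESS 40: (14/32 - 4.8/56) = 35.2% against (15/33 - 3.8/55) = 38.5%, shift +3.4.
- S.c. placebo responder given s.c. active. ESS 20: 34.3% against (14/32 - 2.4/35) = 36.9%, shift +2.6. ESS 40: 35.2% against (14/32 - 3.8/55) = 36.8%, shift +1.7.

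**What grouping as randomised costs.** Suppose response follows the treatment received, at 43% and 7%.

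- One active participant given placebo: (31 × 0.43 + 0.07)/32 - 0.07 = 34.9 points, a loss of 1.1 from 36.
- One placebo participant given active: 0.43 - (15 × 0.07 + 0.43)/16 = 33.75 points, a loss of 2.25.

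Normal-approximation power (two-sided 0.05) falls from 77.7% to 75.1% and 69.6% respectively. Grouped as received, the expected difference stays at 36.0 under the same assumption.

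**The case against.** The SAP follows a rule the protocol already contains. Protocol 12.1 applies treatment received to all sets, and the SAP brings the treatment attribute into line with it. The protocol attribute speaks of randomised treatment that is taken, so it arguably does not say where a participant dosed from the wrong arm belongs; such dosing is not a listed intercurrent event. The SAP's population attribute defines who is included, not how they are grouped. All of this is fair, and the population wording proves little alone. It does not explain why the word randomised was removed, and the two documents still disagree.

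Wrong-arm dosing is unlikely. Route is not blinded, an unblinded pharmacist prepares doses from the allocation list, unblinded monitors check them, and errors are recorded. A full change of group would probably need several wrong doses. The protocol's PD set might also exclude such a participant for a relevant deviation, so the shifts above fit the SAP's version best. These points limit the likelihood; the rule still exists only for the case where dosing goes wrong.

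The large negative shift needs a participant given placebo to respond, about 7 in 100 at the planning rate. Treatment-received grouping keeps the expected difference at 36 points if misdosing is unrelated to prognosis, whereas the as-randomised rule dilutes it. That is a real cost, but the lack of bias rests on that condition and randomisation no longer guarantees it.

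SAP 6.1.3 and Protocol 12.4.2 are largely redacted, so a rationale or an as-randomised sensitivity analysis cannot be excluded. The conflicting sentences themselves are all visible.

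**Conclusion.** The point holds. The protocol's estimand and its grouping rule conflict, and the SAP settles the conflict by altering the estimand. This rests on direct wording and needs no assumption.

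The size is conditional. With no wrong-arm dosing the two rules give identical results. One participant changing group moves the raw difference by about 2 to 7.5 points in either direction. In the three cases recalculated with an assumed placebo prior (mean 7%, ESS 20 or 40), the shift is 1.7 to 4.3 points. These figures rest on assumed counts and a complete change of group. No changed decision can be shown because the criteria are redacted. In a non-confirmatory study this is a modest point, worth correcting because the correction is cheap.

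**What to change.** In Protocol 12.1 and SAP section 4, state that efficacy analyses group treated participants by randomised arm and that only safety and pharmacokinetic analyses use treatment received. In SAP 6.1.1, restore randomised treatment in the treatment attribute so that it matches Protocol 2.1. If any wrong-arm dosing occurs, list it and report as-treated efficacy as a sensitivity analysis.

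If the sponsor prefers treatment received for efficacy, the protocol estimand should be amended openly, with a reason, and an as-randomised sensitivity analysis added. Either way, the rule should be fixed before unblinding.

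The cost is wording in three places, plus the formal amendment that Protocol 14.1 requires for any protocol change. No new data are needed: Protocol 11.2 already has assigned arms tracked in the IRT.
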